4.4 Exclusion criteria

Subjects must not fulfill any of the following exclusion criteria. It is not permitted to waive any of the criteria for any subject:

Disease

- Severe hypertension (grade 3): mean sitting systolic/diastolic BP (SiSBP/SiDBP; measured by OBPM) ≥ 180/110 mmHg, respectively.
- Secondary hypertension (e.g., untreated obstructive sleep apnea, history or presence of drug related hypertension, renal parenchymal disease, renal artery stenosis, primary aldosteronism, thyroid disease (hyper- and hypothyroidism), and pheochromocytoma).
- 3. Known hypertensive retinopathy greater than Keith-Wagener Grade 2.
- 4. Myocardial infarction, percutaneous transluminal coronary angioplasty, or coronary artery bypass graft within 12 months prior to randomization.
- 5. Unstable angina within 6 months prior to randomization.
- 6. Heart failure New York Heart Association class III and IV.
- 7. Valvular defects (such as severe aortic or mitral valve disease) and/or hemodynamically relevant rhythm disturbances.
- 8. Clinical evidence of cerebrovascular insufficiency or a cerebrovascular accident within 6 months prior to randomization.
- 9. *Subjects working night shifts.
- 10. Body mass index $< 20 \text{ kg/m}^2 \text{ or } > 40 \text{ kg/m}^2$

^{*} A maximum of 2 night shifts per week is permitted except within 3 days prior to a study visit.

Essential hypertension Protocol AC-080A201 Version 3 30 May 2016, page 40/112

Confidential

Treatments

- 11. Treatment with any medication which may affect BP (e.g., treatment of psychiatric diseases, ophthalmic preparations); see Appendix 3.
- 11a. Subject with co-morbidities taking anti-hypertensive medications for reasons other than BP.
- 12. Treatment with strong cytochrome P450 3A4 (CYP3A4) isoenzyme inhibitors or inducers; see Appendix 4.
- 13. Treatment with guanethidine and/or mineralocorticoid receptor antagonists within 1 month prior to Screening (Visit 1).
- 14. Treatment with another investigational treatment within 1 month prior to Screening (Visit 1).

Laboratory assessments

- 15. Evidence of the following at Screening (Visit 1)* and Visit 3:
 - a. Hepatic disease: i.e., ALT or AST > 3 times the upper limit of normal range.
 - b. Severe renal impairment, i.e., serum creatinine ≥ 2.26 mg/dl (200 μ mol/l) or creatinine clearance <30 mL/min/1.73 m².
 - c. Hemoglobin <100 g/L.

Others

- 16. Known and documented moderate or severe hepatic impairment.

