11.3.5.2 Laboratory parameters

Descriptive summary statistics by visit and treatment group will be provided for observed values and absolute changes from baseline, in both hematology and blood chemistry and urine (only UACR) laboratory tests. In order to minimize missing data and to allow for unscheduled visits, all recorded assessments will be assigned to the most appropriate visit timepoint according to the best fitting time-window for that assessment.

Actelion internal guidelines will be used for the definitions of marked abnormalities and for the standardization of numeric values obtained from different laboratories and/or using different normal ranges. Standard numeric laboratory variables are transformed to standard units. All laboratory data transferred are taken into account regardless of whether they correspond to scheduled (per protocol) or unscheduled assessments.

Marked laboratory abnormalities will be summarized for each laboratory parameter by treatment group providing their incidence and frequency. Absolute values and changes from baseline of laboratory parameter values during the course of the study will be summarized using the usual location and scale summary statistics by treatment group.

Laboratory parameters include:

- Hematology: hemoglobin, hematocrit, erythrocyte count, leukocyte count with differential counts, platelet count.
- Blood chemistry: AST, ALT, alkaline phosphatase, total and direct bilirubin, LDH, creatinine, creatinine clearance, uric acid, glucose, sodium, potassium, protein, albumin, free T3, free T4, TSH.
- Urine: UACR.

The number and percentage of subjects with treatment-emergent laboratory abnormalities will be tabulated by treatment group.

Essential hypertension Protocol AC-080A201 Version 3 30 May 2016, page 90/112

Confidential

11.3.5.3 12-lead ECG

Descriptive statistics by visit and treatment group will be provided for observed values and absolute changes from baseline, in numeric 12-lead ECG values (PR, QRS, QT, QTcB and QTcF). In order to minimize missing data and to allow for unscheduled visits, all recorded assessments will be assigned to the most appropriate visit time point according to the best fitting time-window for that assessment.

In addition, treatment-emergent morphological ECG abnormalities will be summarized.

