5.6.8.1 Treatment-emergent marked laboratory abnormalities

The marked laboratory abnormalities are given in [Table 2](#), copied from appendix 1 of the protocol.

Table 2 **Thresholds for marked laboratory abnormalities**

Parameter	LL	LLL	HH	HHH	HHHH
Hematology					
Hemoglobin	< 100 g/L (< 10 g/dL; < 6.2 mmol/L)	< 80 (< 8 g/dL; < 4.9 mmol/L;)	Increase in > 20 g/L above ULN or above baseline if baseline is above ULN	Increase in > 40 g/L above ULN or above baseline if baseline is above ULN	
Hematocrit	< 28% for females < 32% for males	< 20%	> 60% in men > 55% in women	> 65%	
Leukocytes	< $3.0 \times 10^9/L$ (< 3000/mm ³)	< $2.0 \times 10^9/L$ (< 2000/mm ³)	> $20.0 \times 10^9/L$ (> 20,000/mm ³)	> $100.0 \times 10^9/L$ (> 100,000/mm ³)	
Platelet count	< $75 \times 10^9/L$ (< 75,000/mm ³)	< $50 \times 10^9/L$ (< 50,000/mm ³)	> $600 \times 10^9/L$	> $999 \times 10^9/L$	
Neutrophils	< $1.5 \times 10^9/L$ (< 1500/mm ³)	< $1.0 \times 10^9/L$ (< 1000/mm ³)	NA	NA	
Eosinophils	NA	NA	> 5.0×10^9 or > 5% (> 5000 cells/mm ³)	NA	
Lymphocytes	< $0.8 \times 10^9/L$ (< 800/mm ³)	< $0.5 \times 10^9/L$ (< 500/mm ³)	> $4.0 \times 10^9/L$ (> 4000/mm ³)	> $20 \times 10^9/L$ (> 20,000/mm ³)	

Parameter	LL	LLL	HH	HHH	HHHH
Blood Chemistry					
AST (U/L)	NA	NA	> 3 × ULN	> 5 × ULN	> 8 × ULN
ALT (U/L)	NA	NA	> 3 × ULN	> 5 × ULN	> 8 × ULN
AP	NA	NA	> 2.5 × ULN	> 5 × ULN	
Bilirubin Total (µmol/L)	NA	NA	> 2 × ULN	> 5 × ULN	
Creatinine	NA	NA	> 1.5 × ULN or > 1.5 × baseline	> 3 × ULN or > 3 × baseline	
Creatinine clearance	< 60 mL/min	< 30 mL/min	NA	NA	
Glucose	< 3.0 mmol /L (< 55 mg/dL)	< 2.2 mmol /L (< 40 mg/ dL)	> 8.9 mmol /L (> 160 mg/dL)	> 13.9 mmol /L (> 250 mg/ dL)	
Sodium		< 130 mmol/L (< 130 mEq/L)	> 150 mmol/L (> 150 mEq/L)	> 155 mmol/L (> 155 mEq/L)	
Potassium	< 3.2(mmol/L)	< 3.0(mmol/L)	> 5.5(mmol/L)	> 6.0(mmol/L)	
Uric acid	NA	NA	> 590 (umol/L) (> 10 mg/dL)	> 720 (umol/L) (> 12 mg/dL)	
Albumin	< 30 g/L (< 3.0 g/dL)	< 20(g/L (< 2.0 g/dL)	-	-	

ALT = alanine aminotransferase; AP = alkaline phosphatase; AST = aspartate aminotransferase; NA = not applicable; ULN = upper limit of normal.

Treatment-emergent marked laboratory abnormalities are those marked abnormalities with onset date after the double-blind treatment start date [see definition in Section 11.2] and before or on double-blind treatment end date [see definition in Section 11.4] plus 30 days (included), that were not present at baseline.

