10.9.4 Laboratory tests

All hematology and chemistry parameters provided by the central and local laboratory are displayed in a subject listing. Marked laboratory abnormalities will be flagged

accordingly. Laboratory values below the limit of detection (i.e., preceded by '<') will be replaced by half that limit in calculations as well as in determining abnormalities.

Hematology, chemistry and urine parameters UACR will be summarized by treatment group for each time window visit. Changes from baseline in these parameters will be summarized for each post-baseline assessment, displaying:

- observed values at baseline and at the post-baseline visit window
- absolute change from baseline to post-baseline visit window

In each evaluation only subjects who had both the assessments at baseline and the considered post-baseline time point are included.

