10.9.4.1 Treatment-emergent marked laboratory abnormalities

For each category (i.e., LL, LLL, HH, HHH, HHHH), treatment-emergent marked laboratory abnormalities [see definition in Section 5.6.8.1] will be summarized by treatment group, displaying counts and percentages of subjects with at least a treatment-emergent marked laboratory abnormality for each parameter for which the marked abnormality is defined. Values from unscheduled visits are included. Subjects may be included in more than one category for the same parameter.

In addition, the number of patients with $ALT > 3 \times$ upper limit of normal (ULN) and bilirubin $> 2 \times$ ULN will be tabulated by treatment group and time point (baseline, Week 8).

Percentages are calculated as number of subjects with at least one abnormality for the parameter under consideration divided by the number of subjects with any post-baseline laboratory measurement.

The distribution of the changes from baseline in hemoglobin will be plotted for each post-baseline visit. As an exploratory analysis, dose trends in the change from baseline to Week 8 in hemoglobin will be analyzed using the MCP-Mod approach. The active comparator will be excluded from these analyses.

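### Treatment-emergent marked laboratory abnormalities are divided by subjects who may already have the abnormality at baseline, so some descriptive percentages understate the incidence of new abnormalities

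*SAP*

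**What the plan says.** SAP 10.9.4.1 takes as numerator the "number of subjects with at least one abnormality for the parameter under consideration", "divided by the number of subjects with any post-baseline laboratory measurement". Counts are made separately for LL, LLL, HH, HHH and HHHH, and "Subjects may be included in more than one category for the same parameter".

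SAP 5.6.8.1 defines which abnormalities count: they must start after the first double-blind dose, fall no later than 30 days after the last one, and be ones "that were not present at baseline".

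The preceding section, SAP 10.9.4, has a stricter rule: "In each evaluation only subjects who had both the assessments at baseline and the considered post-baseline time point are included". It is attached to the observed-value and change-from-baseline summaries, not to the marked-abnormality percentages. Protocol 11.3.5.2 says only: "Marked laboratory abnormalities will be summarized for each laboratory parameter by treatment group providing their incidence and frequency". It gives no denominator.

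**The concern.** The two halves of the percentage refer to different populations. The numerator is specific to parameter and category and leaves out abnormalities present at baseline. The denominator is worded as one figure for all rows and removes neither subjects already in the category nor, read literally, subjects with no post-baseline value of that parameter.

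If a row is read as the risk of developing the abnormality on treatment, it can be too low and never too high, which is the unfavourable direction for a safety table. The shortfall also differs between rows, so rows of one table are not on the same footing.

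**Working it through.** The plan gives no incidence for this output, so there is no stated figure to reproduce.

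**Can subjects be abnormal at baseline?** Compare the entry criteria (Protocol 4.4) with the marked-abnormality limits (SAP Table 2):

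- Creatinine clearance: below 30 is excluded; LL is below 60. Values from 30 to below 60 are admitted.
- Glucose: insulin-dependent diabetes and known, documented uncontrolled diabetes are excluded, but there is no glucose limit; HH is above 8.9 mmol/L.
- Eosinophils HH and lymphocytes HH: no entry limit.
- Hemoglobin: below 100 g/L is excluded, which is the LL limit.
- Aminotransferases: the exclusion is "Hepatic disease: i.e., ALT or AST > 3 times the upper limit of normal range", which is the HH limit.

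The last two exclusions apply at Screening and Visit 3, while baseline is the last value before double-blind treatment. The baseline share in those categories should therefore be about zero, though not strictly zero.

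**Formula.** Let x be the number of subjects with a new abnormality, N the SAP denominator, b the share already in that category at baseline, and m the share with no post-baseline value of that parameter. Taking b and m as independent:

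- SAP percentage = x / N
- At-risk percentage = x / [N(1 − b)(1 − m)]
- SAP percentage = at-risk percentage × (1 − b)(1 − m)

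**Inputs.** N = 490/6 = 81.7, about 82 (490 randomized, SAP 4.2; six equal groups), assuming every subject has some post-baseline laboratory value. For illustration, x = 6. Neither b nor m is in the documents; b is assumed to be 0 to 15%.

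**Results with m = 0.** The SAP shows 6/82 = 7.3% throughout. The at-risk figures are:

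- b = 0: 6/82 = 7.3%
- b = 5%: 82 × 0.95 = 78; 6/78 = 7.7%
- b = 10%: 82 × 0.90 = 74; 6/74 = 8.1%
- b = 15%: 82 × 0.85 = 70; 6/70 = 8.6%

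**Missing values alone (b = 0).** At an assumed m = 2%, 82 × 0.98 = 80.4 and 6/80.4 = 7.5%.

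**Between arms.** Randomization equalizes b in expectation, so only chance imbalance matters. With b = 10%, the baseline count per arm has mean 8.2 and SD √(82 × 0.10 × 0.90) = 2.7, so about 3 to 14 is within chance. An at-risk rate of 8% in both arms would then show as 0.08 × 79/82 = 7.7% or 0.08 × 68/82 = 6.6%. The standard error of an 8% rate with 82 subjects is √(0.08 × 0.92/82) = 3.0 percentage points.

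**The case against.** The strongest reply is that x/N is a legitimate quantity: the proportion of all evaluated subjects who develop a new marked abnormality. The SAP states its denominator openly, and randomization protects the comparison between arms. This stands in part: the figure is wrong only as a measure of risk among those who could develop the abnormality. But that is the natural reading of a treatment-emergent incidence, and the protocol asks for incidence.

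Four stronger readings are tempting, and the documents do not support them.

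- A reader might infer that the main laboratory safety comparison across doses is biased. SAP 13.11 does not flag HEM_TEMA or CHE_TEMA as key; its key laboratory tables are HEM_CHG and UACR_CHG, both changes from baseline. The laboratory dose-response analysis concerns change in hemoglobin, and no test is attached to these percentages. Any distortion between arms comes from chance imbalance and, in the example above, is well inside sampling error.
- A reader might infer that all rows are understated. Hemoglobin LL and ALT/AST HH are practically unaffected because their limits are also entry exclusions.
- A reader might infer that a subject abnormal at baseline can never be counted. That is true only within the same category: a subject at HH can still become a new HHH.
- A reader might infer that many subjects without a value are counted as normal. This depends on taking the denominator wording literally, when it may mean any measurement of the parameter in question. The share is probably small in any case, since one blood sample per visit serves both hematology and chemistry (Protocol 7.3.5.2) and lost samples are to be collected again (Protocol 7.3.5.1).

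Individual values are listed with marked abnormalities flagged, so a careful reader could reconstruct the at-risk numbers. The table layouts follow a standard outside these documents, so n/N may already be shown. Neither point changes the stated denominator.

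**Conclusion.** Wrong as written, but minor. For categories without a matching entry limit, the SAP percentage equals the incidence of new abnormalities multiplied by (1 − b), so the relative understatement is b itself. Over the assumed range of 0 to 15%, a displayed 7.3% corresponds to 7.3% to 8.6%. The direction follows from SAP 5.6.8.1 and 10.9.4.1 together; the size rests on an assumed b, because the documents give no baseline prevalence. No hypothesis test, type I error, sample size or key output is affected.

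**What to change.** In SAP 10.9.4.1, define the denominator for each parameter and category as the subjects with at least one post-baseline value of that parameter in the treatment-emergent window who were not in that category at baseline. State how subjects with no baseline value are handled, and show n/N on each row of HEM_TEMA and CHE_TEMA.

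The cost is a short change to the SAP text and a changed denominator in two table programs. The downside is that N varies by row, so a single column total no longer serves the whole table.

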10.9.5 Physical examination, vital signs and body weight

Physical examination data performed during the course of the study will be reported in a subject listing. Pulse rate and body weight measurements will be reported in a subject listing and summarized by time window visit.

Furthermore, for each post-baseline assessment, average PR (from BpTRU[®]) and body weight will be summarized displaying, for each treatment group, descriptive statistics for:

- observed values at baseline and at the post-baseline visit window
- absolute change from baseline to post-baseline visit window

In each evaluation only subjects who had both the assessment at baseline and the considered post-baseline assessment are included. Only measurements obtained in sitting position will be taken into account.

The density of the changes from baseline in body weight will be plotted for each post-baseline visit. As an exploratory analysis, dose trends in the change from baseline to Week 8 in body weight ([kg]) will be analyzed using the MCP-Mod approach. The active comparator will be excluded from these analyses.

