7.2.1.1 Office blood pressure measurement

Systolic and diastolic BP will be measured non-invasively at each study visit.

OBPM is the mean of multiple BP readings recorded with a fully automated device with the patient resting quietly in the office/clinic. It has several advantages over manual BP measurements, especially in routine clinical practice, by virtually eliminating office-induced increases in BP, improving accuracy, minimizing observer error, and providing a more standardized measurement technique [Myers 2010].

The OBPM device is the BpTRU (
), which will be provided to each site by the central BP laboratory for the duration of the study.

Sitting BP measurement

At each pre-dose assessment, SiSBP and SiDBP will be measured at a pre-defined number of readings. There is a preset interval between measurements (timed from the start of one reading to the start of the next one). The first reading will be discarded and the mean of the remaining readings will be the mean sitting OBPM value [Myers 2006, Myers 2008].

The BpTRU device is an automatic oscillometric sphygmomanometer designed to record an initial 'test' reading and then a series of readings [Myers 2006, Myers 2008]. Prior to

Essential hypertension Protocol AC-080A201 Version 3 30 May 2016, page 58/112

Confidential

the measurement, the subject has to rest in a sitting position for a minimum of 5 minutes in a quiet room.

Standing BP measurement

BP must be measured in the standing position to monitor orthostatic hypotension [see Section 7.3.1.1]. Standing SBP/DBP is measured by OBPM device (BpTRU) automatically twice, approximately one and three minutes after standing.

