7.3.1 Vital signs

7.3.1.1 Orthostatic hypotension

At each study visit standing SBP and DBP will be measured with the OBPM device (i.e., BpTRU) in addition to sitting measurements [see Section 7.2.1.1].

Orthostatic hypotension is defined as a BP decrease of SBP \geq 20 mmHg or DBP \geq 10 mmHg from sitting to standing position with symptoms of cerebral hypo-perfusion (e.g., light-headedness, dizziness, pre-syncope). The last SiDBP and SiSBP values measured by OBPM are compared to the last measured standing BPs.

Any value meeting the criteria of orthostatic hypotension must be recorded as an AE.

7.3.1.2 **Heart rate**

At each visit, HR will be measured with the OBPM device (i.e., BpTRU) at the same time as BP measurements, in the sitting position. The last HR measurement will be used for analysis.

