11.3.5.4 Vital signs and body weight

Vital signs parameters, HR and body weight will be summarized at each study visit using the usual location and scale summary statistics by treatment group for both absolute values and changes from baseline. Subjects for whom no post-baseline value is available are excluded from the analysis of the changes from baseline.

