5.6.6 Physical examination, vital signs and body weight

Vital signs include PR measured by BpTRU[®] (simultaneously with BP; the mean is provided in the same way, i.e., based on the last 5 of 6 measurements) and body weight (DBP and SBP are evaluated as efficacy endpoints). For PR, the value is retrieved from the SDTM VS domain by selecting VSTESTCD = “HR” and VSSCAT = ‘Average’.

All assessments (including the unscheduled ones) are considered and re-assigned to the most appropriate visit according to the time windows described in Section 12.

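### Standing blood pressure is measured at every visit to monitor orthostatic hypotension, but the SAP plans no summary or listing of it

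*SAP*

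**What the plan says.** Protocol 7.2.1.1 gives the purpose of the measurement: "BP must be measured in the standing position to monitor orthostatic hypotension". It also gives the timing: "Standing SBP/DBP is measured by OBPM device (BpTRU) automatically twice, approximately one and three minutes after standing". Protocol 7.3.1.1, which sits under vital signs within the safety assessments, sets the frequency: "At each study visit standing SBP and DBP will be measured with the OBPM device".

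The same section defines orthostatic hypotension as a fall of at least 20 mmHg systolic or 10 mmHg diastolic on standing, accompanied by symptoms of reduced cerebral perfusion. It names the readings to use: "The last SiDBP and SiSBP values measured by OBPM are compared to the last measured standing BPs". A value that meets the definition has to be reported as an adverse event.

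On analysis, protocol 11.3.5.4 says: "Vital signs parameters, HR and body weight will be summarized at each study visit", by treatment group, as values and as changes from baseline. SAP 5.6.6 narrows vital signs to pulse rate and body weight, and sets blood pressure aside with the remark that "DBP and SBP are evaluated as efficacy endpoints". SAP 10.9.5 summarizes pulse rate and weight and adds: "Only measurements obtained in sitting position will be taken into account".

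**The concern.** The efficacy variables in SAP 5.5 are sitting office readings or ambulatory recordings. Once 5.6.6 sends blood pressure to efficacy, standing pressure therefore belongs to neither the efficacy nor the safety analysis. A safety measurement made at every visit, for a stated purpose, disappears between the two halves of the plan.

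This is a dose-finding study. Protocol 1.3 says doses will be chosen on the balance of efficacy and tolerability, and protocol 2.2 makes the safety and tolerability of the four doses a secondary objective. For a drug meant to lower blood pressure, a by-arm view of postural change is direct tolerability evidence. SAP 4.1.3 adds exploratory dose-response analyses for hemoglobin and body weight because they bear on safety, yet postural pressure gets not even a listing. Home readings do not fill the gap, since protocol 7.2.2 keeps them out of the eCRF.

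**Working it through.** This is mainly a text check. The plan states no orthostatic rate, power or sample-size figure to reproduce.

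**Following standing pressure from collection to output**

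1. *Collection.* Two standing readings at each study visit (protocol 7.2.1.1 and 7.3.1.1).
2. *Endpoints.* Protocol 6.2 and 11.2.4 name changes in body weight and heart rate. Neither names standing pressure or postural change.
3. *Protocol analysis.* Section 11.3.5.4 lists vital signs parameters alongside heart rate and weight. Section 7.3.1 has only two subsections, orthostatic hypotension and heart rate. With heart rate named separately, the natural reading is that the remaining vital sign is blood pressure, including the postural comparison. The term is not defined, however.
4. *SAP definition.* Section 5.6.6 restricts vital signs to pulse rate and weight.
5. *SAP tables and figures.* Section 13.12 covers pulse rate, body weight and physical findings. The office-pressure tables and figures in 13.6 and 13.7 are for sitting values.
6. *SAP listings.* The vital-signs listing in 13.12 covers pulse rate and weight. The office-pressure listing in 13.7 covers sitting diastolic pressure, sitting systolic pressure and pulse rate. SAP 10.9 nevertheless says that all safety data will be listed, as does protocol 11.3.5.
7. *Declared changes.* SAP 4.1.3 declares only the added hemoglobin and weight analyses.
8. *Adverse-event route.* SAP 10.9.1 and 13.9.1 tabulate treatment-emergent events by treatment group and preferred term, so reported postural events are seen by dose.

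**What each route shows by arm**

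| Situation | Planned output |
|---|---|
| Symptomatic fall meeting 7.3.1.1 | Adverse-event tables |
| Symptomatic fall at one minute, recovered by three | Outside the 7.3.1.1 definition, but the symptom (such as dizziness) is reportable under protocol 10.1.1 and tabulated |
| Fall without symptoms, judged clinically significant | Reportable under 10.1.1 as an abnormal assessment |
| Fall without symptoms, not so judged | None |
| Average size of standing-minus-sitting change | None |

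**How much data is involved**

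Inputs: 490 randomized subjects (SAP 4.2); three double-blind visits after baseline, at Weeks 2, 4 and 8 (protocol Table 1); two standing readings per visit (protocol 7.2.1.1).

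- Double-blind standing readings: 490 × 3 × 2 = 2,940.
- Per arm, with six arms: 2,940 / 6 = 490.
- One-minute readings among them, which the definition does not use when both readings are taken: 490 × 3 × 1 = 1,470.

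These are upper bounds that assume no dropout and no missed visit, and they include the placebo and lisinopril arms. They count unused readings, not missed events.

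**The case against.** The strongest reply is that nothing pre-specified has been lost. Standing pressure is not a named safety endpoint. The protocol collects it to monitor a clinical event, routes that event to adverse-event reporting, and the events are tabulated by arm. Much of this stands, and it rules out several stronger readings.

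- *That orthostatic falls cannot be compared across doses.* A reader might infer this, but symptomatic falls, and symptoms such as dizziness, reach the adverse-event tables by treatment group. The readings also exist, so the comparison of measured falls is unplanned rather than impossible.
- *That SAP 10.9.5 itself strips out standing pressure.* The sitting-only sentence ends a paragraph on pulse rate and body weight, and it does not mention blood pressure.
- *That protocol 7.3.1.1 contradicts itself* by requiring any qualifying value to be reported while using only the last readings. The definition and the readings to compare come first, and the reporting rule then applies them.
- *That Phase 1 showed a postural pressure signal.* Protocol 1.2.1 reports postural orthostatic tachycardia, not a pressure fall. It followed single doses of up to 600 mg, and 600 / 50 = 12 times the top dose here. After multiple dosing the commonest events were headache, somnolence and nasal congestion, and apart from the hemoglobin and body-weight changes no clinically relevant vital-sign finding is reported.
- *That the readings are insensitive because they are pre-dose.* With a half-life of about 44 hours and roughly three-fold accumulation, the documents do not support this.

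The reply does not explain why safety data collected at every visit have no listing when the SAP says all safety data will have one, or why the narrowing of vital signs is not declared.

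**Conclusion.** The point holds as a reporting gap in the safety analysis. The SAP plans no table, figure or listing of standing pressure or of postural change. That conflicts with its own listing commitment in 10.9, departs from the natural reading of protocol 11.3.5.4, and is not declared in 4.1.3. By dose, only what is reported as an adverse event will be visible. Falls without symptoms that are not judged clinically significant, and the magnitude of postural change, will not be compared between arms.

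Up to 2,940 double-blind readings are affected. The number of falls that would go unseen cannot be estimated, because the documents give no rate. The primary objective and the efficacy analyses are untouched. This is a cheap improvement to the tolerability evidence, not a flaw that endangers the trial's conclusions.

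The conclusion rests on two assumptions. Vital signs in protocol 11.3.5.4 is taken to include the blood pressure described under protocol 7.3.1. The standing readings are assumed to be in the transferred data: protocol Table 1 marks office blood pressure as sent electronically, but SAP 5.5 describes the transfer only for the sitting measurements.

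**What to change.** Change the analysis only, in SAP 5.6.6, 10.9.5 and 13.12:

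- Add a descriptive table on the Safety Set, by arm and visit, of standing-minus-sitting systolic and diastolic pressure at each of the two standing readings. State the sitting reference. The last sitting reading is the protocol's own comparator, and SAP 5.5 says the individual sitting measurements are transferred.
- In the same table, count subjects who cross the protocol's own thresholds of 20 mmHg systolic or 10 mmHg diastolic, with and without an associated adverse event.
- Add a listing of standing pressure.
- Make clear in 10.9.5 that the sitting-only sentence applies to pulse rate and does not govern this table.

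If the sponsor prefers not to add these outputs, SAP Section 4.1 should declare and justify the omission against protocol 11.3.5.4, and the listing statement in 10.9 should be amended to match.

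The protocol's clinical definition of orthostatic hypotension and its adverse-event rule stay as they are. SAP 4.2 shows that the database was already locked, so altering that rule could not change what was recorded in any case.

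The cost is one exploratory table and one listing, with no new procedure and no effect on type I error for the main analysis. The downside is that some falls without symptoms will be displayed and will need a sentence of interpretation.
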